### **1.8.1 Summary of Benefits and Risks**

Cabozantinib and the combination of nivolumab and ipilimumab have each demonstrated clinical activity in previously untreated intermediate- and poor-risk RCC patients, and cabozantinib in combination with nivolumab has demonstrated activity across all risk groups. In addition, preliminary clinical data suggest that cabozantinib in combination with nivolumab and ipilimumab exhibits clinical activity. Therefore, based on preclinical observations, the demonstrated clinical activity of nivolumab and ipilimumab and of cabozantinib in this patient population, and the known safety profiles of these agents, the potential benefits of evaluating these agents outweigh the potential risks.

### **1.9 Study Conduct**

This study will be conducted in compliance with Good Clinical Practice (GCP), including International Conference on Harmonisation (ICH) Guidelines and also consistent with the most recent accepted version of the Declaration of Helsinki. In addition, all applicable local laws and regulatory requirements relevant to the use of new therapeutic agents in the countries involved will be adhered to.

The study will be conducted in compliance with the protocol. The appropriate Institutional Review Boards (IRBs) or Ethics Committees (ECs) must approve the protocol, any amendments, and the subject informed consent form (ICF) prior to implementation.

Freely given written informed consent must be obtained from every subject prior to participation in this clinical trial. The rights, safety, and well-being of participating subjects are the most important considerations and should prevail over interests of science and society.

Study personnel involved in conducting this trial will be qualified by education, training, and experience to perform their respective task(s). This trial will not use the services of study personnel for whom sanctions have been invoked or there has been scientific misconduct or fraud (eg, loss of medical licensure, debarment, etc).

## **2 STUDY OBJECTIVES AND ENDPOINTS**

### **2.1 Objectives**

The objective of this study is to evaluate the efficacy and safety of the combination of cabozantinib with nivolumab and ipilimumab versus the combination of nivolumab and ipilimumab in previously untreated subjects with intermediate- and poor-risk advanced or metastatic RCC.

CONFIDENTIAL

Protocol XL184-313 Protocol Amendment 3.0  
Page 45 of 193

## 2.2 Endpoints

### *Primary Efficacy Endpoint:*

- Duration of PFS, per Response Evaluation Criteria in Solid Tumors version 1.1 (RECIST 1.1), by Blinded Independent Radiology Committee (BIRC)

### *Secondary Efficacy Endpoint:*

- Duration of OS

### *Additional Endpoints:*

- ORR per RECIST 1.1 by BIRC
- PFS and ORR per RECIST 1.1 by BIRC according to PD-L1 status
- PFS and ORR per RECIST 1.1 as assessed by the Investigator
- Duration of radiographic response as assessed by the Investigator and by BIRC
- Safety through the evaluation of AEs, including irAEs, and other safety assessments.
- Pharmacokinetics (PK) of cabozantinib given in combination with nivolumab and ipilimumab
- Immunogenicity of nivolumab and ipilimumab given in combination with cabozantinib
- Correlation of biomarker analyses with clinical outcomes
- Health-related quality of life (HRQoL) as assessed by the EuroQol Health questionnaire instruments (EQ-5D-5L)
- Health care resource utilization

CONFIDENTIAL

Protocol XL184-313 Protocol Amendment 3.0  
Page 46 of 193

### **3 STUDY DESIGN**

#### **3.1 Study Sites**

This study will be conducted at approximately 180 sites.

#### **3.2 Estimated Study Dates and Duration of Subject Participation**

It is estimated that 21 months will be required to randomize 840 subjects. The number of events required for the primary analysis of PFS (249 events among the first 440 subjects randomized) is expected to be observed approximately 23 months after the first subject is randomized. The number of events required for the final analysis for the secondary endpoint of OS (433 events among 840 subjects) is expected to be observed approximately 69 months after the first subject is randomized. The true intervals required to meet these milestones may be longer or shorter due to divergence from assumptions, including non-constant accrual rate due to the time required for all study sites to become active. The estimates for the timing of event-driven analyses do not include the additional months required for event ascertainment, data quality review, data analysis and interpretation.

It is estimated that subjects will participate for an average of 12-18 months on study treatment. Some study assessments continue periodically after study treatment is discontinued, and subjects will be followed until death, withdrawal of consent, or Sponsor decision to no longer collect these data.

#### **3.3 Overview of Study Design**

This is a Phase 3 multicenter, randomized, double-blind, controlled trial of cabozantinib with nivolumab and ipilimumab vs nivolumab and ipilimumab in subjects with intermediate or poor risk advanced or metastatic RCC not previously treated with systemic therapy. The primary efficacy endpoint is BIRC-determined PFS. Cabozantinib-matched placebo will be given in combination with nivolumab and ipilimumab in the control arm to mask (blind) the study treatment. Approximately 840 eligible subjects will be randomized to receive study treatment as described in [Figure 3-1](#) and [Section 3.4](#).

The study was originally designed to enroll 676 subjects; the sample size was increased to accommodate new, external data about the expected median overall survival in the control arm (see [Section 9.5](#)).

The PITT population may be expanded by 25% from the first 440 to the first 550 randomized if a review of accumulating PFS events suggests that the 249 events required for the analysis will not

[figure not shown]
CONFIDENTIAL

Protocol XL184-313 Protocol Amendment 3.0  
Page 47 of 193

be reached due to censoring caused by a higher than expected study drop-out or non-compliance stemming from the COVID-19 pandemic.

Special accommodations during the global COVID-19 pandemic are described in [Appendix K](#).

**Figure 3-1: XL184-313 Study Schema**

IMDC, international metastatic renal cell carcinoma database consortium; IV, intravenous; PO, oral administration; qd, once daily; q3(4)w once every 3(4) weeks; RECIST, response evaluation criteria in solid tumors; RCC, renal cell carcinoma

Each subject's course of treatment will consist of the following periods:

**Pre-Treatment Period:** Potential subjects will be screened to determine whether they meet the required eligibility criteria. Qualifying screening assessments must be performed within 28 days before randomization unless otherwise specified.

**Treatment Period:** Subjects who meet all study eligibility criteria will be randomly assigned in a 1:1 fashion to receive either cabozantinib in combination with nivolumab and ipilimumab or placebo in combination with nivolumab and ipilimumab. Details about the investigational regimens are provided in [Section 6](#).

Subjects will receive study treatment as long as they continue to experience clinical benefit in the opinion of the Investigator or until unacceptable toxicity, the need for subsequent systemic anti-cancer treatment, or until any other reasons for treatment discontinuation listed in the protocol ([Section 3.6](#)). Treatment may continue after radiographic progression per RECIST 1.1 as long as the Investigator believes that the subject is still receiving clinical benefit from study

treatment and that the potential benefit of continuing study treatment outweighs potential risks ([Section 5.7.6.2](#)).

**Transition to Unblinded Treatment:** The study may transition to unblinded treatment at the discretion of the Sponsor and upon any necessary discussions with regulatory authorities after analyses of PFS and OS have been performed. If the study is declared futile or the null hypothesis for the primary endpoint of PFS is not rejected (negative study), the study will be unblinded and investigators and subjects will be notified. If the null hypothesis for the primary endpoint of PFS is rejected (positive study), the study will not be unblinded until the null hypothesis for the secondary endpoint of OS is rejected or the final analysis of OS is performed.

Once the study transitions to unblinded treatment, investigators and subjects will be notified of the randomized treatment assignment to allow for appropriate treatment decisions. Protocol procedures and assessments will continue without change.

**Post-Treatment Period:** Subjects who discontinue from study treatment (including subjects in the Maintenance Phase [below]) will return to the site for two follow-up visits for safety assessments. The first Post-Treatment Follow-up Visit (FU-1) for safety is to occur 30 (+14) days after the date of the decision to permanently discontinue study treatment (defined as the later of the decision to permanently discontinue study treatment or the last dose of study treatment). A second follow-up visit (FU-2) will be conducted approximately 100 ( $\pm 14$ ) days after the date of the decision to permanently discontinue study treatment. Radiographic tumor assessments and HRQOL assessments are to continue, regardless of whether study treatment is given, reduced, held or discontinued until a protocol-defined criterion for ending radiographic assessments is met. Consequently, these assessments may be required in the Post-Treatment Period for some subjects.

In addition, subjects are to be contacted every 12 weeks ( $\pm 14$  days) after the 100-day Post-Treatment Follow-Up Visit (FU-2) to assess survival status and document receipt of systemic nonprotocol anti-cancer therapy (NPACT). This will continue until the subject expires or the Sponsor decides to discontinue collection of these data. Further, coinciding with each analysis of OS, sites will be required to determine the survival status for all subjects not known to be deceased as of the data cutoff date for the analysis. This will require additional subject contacts outside the 12-week schedule. Every effort must be made to collect this protocol-specific information unless consent for non-interventional study assessments is withdrawn. Assessments of OS/NPACT are not required in the Maintenance Phase (below).

CONFIDENTIAL

Protocol XL184-313 Protocol Amendment 3.0  
Page 49 of 193

**Study Completion:** The study will be considered complete if any of the following criteria apply:

- futility analysis of PFS: the trial has been declared futile by the Sponsor, or
- primary analysis of PFS: null hypothesis is not rejected, or
- primary analysis of PFS: null hypothesis is rejected for PFS and the null hypothesis is rejected for OS (or the final planned analysis for OS has been conducted)

**Maintenance Phase/Treatment After Study Completion:** The purpose of the Maintenance Phase is to continue to provide long-term access to study drug(s) to subjects who are deriving clinical benefit even after the study objectives have been completed (Study Completion, see above). When sufficient data have been collected to adequately evaluate all study endpoints, and after treatment assignment has been unblinded, the Sponsor may initiate a Maintenance Phase. Upon initiation of the Maintenance Phase, the Sponsor considers the safety and efficacy profile of the experimental treatment regimen within this study to have been sufficiently established, and data analyses required for regulatory purposes have been completed. The Sponsor is to notify the sites if or when the study will enter the Maintenance Phase or if an alternative post-Study Completion option will be implemented ([Section 6.3](#)).

In the Maintenance Phase, subjects on active study treatment will continue to receive study treatment until they meet the protocol-required criteria for treatment discontinuation. Subjects in the Maintenance Phase are to undergo periodic safety assessments (including local laboratory tests) and tumor assessments. The nature and frequency of these assessments during the Maintenance phase are to be performed per institutional standard of care and guidance from the Sponsor as necessary (see [Appendix B](#)). It is the Investigator's responsibility to ensure that subject visits occur frequently enough and adequate assessments are performed to ensure subject safety.

In order to continue to collect important safety information for subjects enrolled in the study during the Maintenance Phase, reporting of SAEs; certain AEs (including AESIs [whether serious or not], and AEs leading to dose modifications or treatment discontinuation); and other reportable events (drug-induced liver injury [DILI], pregnancy, and medication errors with sequelae) is to continue per protocol requirements specific to the Maintenance Phase.

The study clinical database will be closed upon initiation of the Maintenance Phase. Important safety information (noted above) collected in the Maintenance Phase will be captured in the safety database. Only data collected prior to implementation of Maintenance Phase will be reported in a clinical study report.

CONFIDENTIAL

Protocol XL184-313 Protocol Amendment 3.0  
Page 50 of 193

**End of Trial:** End of trial is defined as the last scheduled visit or scheduled procedure for the last subject (including Maintenance Phase assessments).

### 3.4 Treatment Groups and Randomization

After obtaining informed consent, the site representative will use the designated web-based interactive response technology (IRT) system to register a subject. The IRT will assign a unique subject number. When a subject has been deemed eligible at the study site, the site representative will use the IRT to randomize and enroll the subject into the study.

Eligible subjects will be randomly assigned in a 1:1 ratio to the following treatment arms:

- Experimental arm:  
Cabozantinib (40 mg oral, once daily [qd]) + nivolumab (3 mg/kg infusion, once every 3 weeks [q3w]) x 4 doses + ipilimumab (1 mg/kg infusion, q3w) x 4 doses, followed by cabozantinib (40 mg oral qd) + nivolumab infusion (480 mg flat dose q4w). Nivolumab will be administered for a maximum of 2 years.
- Control arm:  
Cabozantinib-matched placebo (oral, qd) + nivolumab (3 mg/kg infusion, q3w) x 4 doses + ipilimumab (1 mg/kg infusion, q3w) x 4 doses, followed by cabozantinib-matched placebo (oral, qd) + nivolumab infusion (480 mg flat dose q4w). Nivolumab will be administered for a maximum of 2 years.

Details about treatment regimens are provided in [Section 6](#).

Randomization will be stratified by the following factors established at screening:

- IMDC prognostic score (1-2 risk factors [intermediate] vs 3-6 risk factors [poor])
- Region ([US or Canada or Europe or Australia or New Zealand] vs [Latin America or Asia])

The IMDC risk factors are (Heng et al 2009):

- Karnofsky performance status (KPS) < 80%
- Less than 1 year from initial RCC diagnosis (including original localized disease if applicable) to systemic treatment
- Hemoglobin < lower limit of normal (LLN)
- Corrected calcium > 10 mg/dL
- Absolute neutrophil count (ANC) > upper limit of normal (ULN)
- Platelet count > ULN

CONFIDENTIAL

Protocol XL184-313 Protocol Amendment 3.0  
Page 51 of 193

The most recent evaluations used to establish eligibility must be used to determine the risk factor category for stratification. Results from the central laboratory should be used for these purposes whenever possible. Local laboratory results for stratification will be allowed in instances where a central laboratory result has not been obtained and would delay randomization approval, or for laboratory values that are required to be repeated closer to randomization. Results from local laboratory assessments used to determine the appropriate stratification values are to be documented in source materials and carefully reviewed by site personnel before entry into the IRT for randomization and sent to the local laboratory management vendor of the study.

Randomization should occur as close as possible to the planned start of treatment (ie, within 3 days). Subjects are defined as enrolled in the study if randomized. Changes to stratification values entered in the IRT will not be performed after randomization. Randomization will not be voided except under very rare circumstances and with Sponsor approval. Subjects who sign consent, are assigned a subject identifier, and are screened (to any degree, including rescreening) but never randomized are deemed permanent screen failures.

### **3.5 Study Blinding**

#### **3.5.1 Blinding of Study Treatments**

The cabozantinib-matched placebo will be given in combination with nivolumab and ipilimumab in the control arm to blind (mask) study treatment.

Study treatment assignment will be unknown to the subjects, investigators, study centers, Sponsor, and any contract research organization (CRO) affiliated with the study other than those authorized to access treatment assignment for regulatory safety reporting and submission processes (see [Section 8.2.2](#)), IRT administration, and drug supply management.

Cabozantinib-matched placebo will be packaged and color-, size-, and shape-matched to be indistinguishable from cabozantinib ([Section 6.1](#)).

#### **3.5.2 Unblinding Procedure for Individual Subjects**

Blinding of oral study treatment is critical to the integrity of this clinical study and therefore if a subject's treatment assignment is disclosed to the study site the subject will have all study treatment discontinued. In the event of a medical emergency, the treating physician may decide that knowledge of the investigational product is critical to the subject's management of that emergency. In this rare situation, the treating physician may access the treatment information for this subject through the IRT system. The blind should only be broken for the specific subject in question and, before breaking the blind of an individual subject's study treatment, the

CONFIDENTIAL

Investigator should have determined that the information will alter the subject's immediate medical management. In the vast majority of cases, AEs may be properly managed without the need for unblinding (see [Section 6.6](#)). An unblinded notification including the subject ID, treatment arm, and date of unblinding will be provided to the Investigator.

### **3.6 Treatment Discontinuation and Study Withdrawals**

Details for handling treatment discontinuation and study withdrawal are discussed in [Sections 3.6.1](#) and [3.6.2](#), respectively.

If a subject requests to discontinue study treatment and/or withdraws study consent, the Investigator must establish the specific nature of the subject's request.

The subject's decisions for each individual component of study treatment (there may be more than one decision over time) must be recorded in source documents and transcribed to study case report forms (CRFs).

#### **3.6.1 Treatment Discontinuation**

Subjects will receive study treatment until treatment discontinuation for any of the reasons listed below. Subjects may discontinue study treatment and assessments or withdraw their consent to participate in the study at any time without prejudice. If a subject discontinues all study treatment, the reason will be documented in source documents and all study treatment will be stopped. The investigator may also discontinue a subject from all study treatment if in his or her clinical judgment it is in the best interest of the subject or if the subject cannot comply with the protocol. In addition, the Investigator will also discontinue a subject from study treatment upon the Sponsor's request or if the Sponsor chooses to terminate the study.

The following are possible reasons for discontinuation of all study treatment:

- Subject no longer experiences clinical benefit as determined by the Investigator (eg, disease progression [PD] and/or clinical deterioration attributable to PD where either is unlikely to reverse with continued study treatment and/or supportive care).
- Unacceptable side effects the Investigator feels may be due to study treatment. Continuation of one component of the combination study treatment while discontinuing the other will be allowed. The Investigator is encouraged to discuss such circumstances with the Sponsor.
- The investigator feels it is not in the best interest of the subject to continue on study.

CONFIDENTIAL

Protocol XL184-313 Protocol Amendment 3.0  
Page 53 of 193

- Subject participation in another clinical study using an investigational agent, investigational medical device, or other intervention.
- Necessity for treatment with non-protocol systemic anti-cancer therapy.
- Necessity for interrupting all study treatment for greater than 12 weeks for study-treatment related AEs unless approved by the Sponsor. (Note: temporary interruptions of study treatment for greater than 12 weeks due to the effects of COVID-19 and unrelated to AEs are described in [Appendix K](#).)
- Refusal of sexually active fertile subjects to use highly effective methods of contraception (defined in [Appendix D](#)).
- Female subjects who become pregnant.
- Request by the Sponsor
- Unblinding of study treatment by the Investigator (prior to unblinding of study treatment for all subjects)
- Subject request to discontinue all study treatments (with or without concurrent withdrawal of informed consent).
- Significant noncompliance with the protocol schedule in the opinion of the Investigator or the Sponsor.
- Subject is determined to have been randomized to receive placebo following study-wide unblinding

In addition, specific criteria for discontinuation of cabozantinib are provided in [Section 6.6.2](#) and for discontinuation of nivolumab/ipilimumab are provided in [Section 6.6.3.2](#). The maximum treatment period for nivolumab/ipilimumab is specified in [Section 3.4](#).

To ensure timely Sponsor notification of study treatment discontinuations, site personnel are to promptly record treatment discontinuations in the study IRT. The reason for study treatment discontinuation must be recorded in source documents and CRFs. If a subject fails to return for the protocol-defined visits, an effort must be made to determine the reason. If the subject cannot be reached by telephone, at the minimum a registered letter requesting contact with the clinic should be sent to the subject (or the subject's legal guardian).

For subjects who discontinue study treatment, every effort must be made to undertake protocol-specified follow up procedures including end of treatment assessments, survival

CONFIDENTIAL

Protocol XL184-313 Protocol Amendment 3.0  
Page 54 of 193

follow-up, and documentation of subsequent anti-cancer treatment(s) unless consent for non-interventional study assessments is also withdrawn.

If a subject is discontinued from study treatment because of an AE (including AESI; [Table 8-1](#)) considered to be related to study treatment, the event must be followed until resolution or determination by the Investigator that the event has become stable or irreversible.

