### **5.3 Transition to Unblinded Treatment**

The study may transition to unblinded treatment at the discretion of the Sponsor and upon any necessary discussions with regulatory authorities after analyses of PFS and OS have been performed. If the study is declared futile or the null hypothesis for the primary endpoint of PFS is not rejected (negative study), the study will be unblinded and investigators and subjects will be notified. If the null hypothesis for the primary endpoint of PFS is rejected (positive study), the study will not be unblinded until the null hypothesis for the secondary endpoint of OS is rejected or the final analysis of OS is performed.

Once the study transitions to unblinded treatment, investigators and subjects will be notified of the randomized treatment assignment to allow for appropriate treatment decisions. Protocol procedures and assessments will continue without change.

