## **5.5 Maintenance Phase/Treatment After Study Completion**

The purpose of the Maintenance Phase is to continue to provide long-term access to study drug(s) to subjects who are deriving clinical benefit even after the study objectives have been completed (Study Completion, see [Section 3.6.3](#)). When sufficient data have been collected to adequately evaluate all study endpoints, and after treatment assignment has been unblinded, the Sponsor may initiate a Maintenance Phase. Upon initiation of the Maintenance Phase, the Sponsor considers the safety and efficacy profile of the experimental treatment regimen within this study to have been sufficiently established, and data analyses required for regulatory purposes have been completed. The Sponsor is to notify the sites if or when the study will enter

the Maintenance Phase or if an alternative post-Study Completion option will be implemented ([Section 6.3](#)).

In the Maintenance Phase, subjects on active study treatment will continue to receive study treatment until a criterion for protocol-defined discontinuation has been met ([Section 3.6.1](#)). Subjects in the Maintenance Phase are to undergo periodic safety assessments (including local laboratory tests) and tumor assessments ([Appendix B](#)). The nature and frequency of these assessments are to be performed per institutional standard of care and guidance from the Sponsor as necessary. It is the Investigator's responsibility to ensure that subject visits occur frequently enough and adequate assessments are performed to ensure subject safety.

In order to continue to collect important safety information on subjects still enrolled in the study, reporting of SAEs, AESIs, and other reportable events (DILI, pregnancy, and medication errors with sequelae) is to continue per protocol ([Section 8.2](#)).

Further, the following AEs, whether serious or not, are to be reported using the same process as for reporting SAEs described in the protocol [Section 8.2](#) (though SAE reporting timeline requirements do not apply to non-serious events reported in these categories):

- Adverse events of special interest (AESIs)
- Adverse events, whether serious or not, leading to study treatment discontinuation
- Adverse events, whether serious or not, leading to study treatment dose modification (ie, causing study treatment to be interrupted, delayed, or reduced)

Study drug accountability is to continue as described in [Section 6.5](#).

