### **6.3 Treatment After Study Completion**

After study completion (see [Section 3.6.3](#)), subjects who continue to demonstrate clinical benefit may be eligible to receive Exelixis-supplied study treatment for the maximum treatment duration specified in [Section 6.2](#) during the Maintenance Phase. Alternatively, study treatment may be provided via a rollover study requiring approval by responsible health authority and ethics committee or through another mechanism at the discretion of Exelixis.

Exelixis reserves the right to terminate access to Exelixis-supplied study treatment if any of the following occur:

- a) the study is terminated due to safety concerns;
- b) the development of nivolumab, ipilimumab, or cabozantinib is terminated for other reasons, including but not limited to lack of efficacy and/or not meeting the study objectives (eg, study is declared futile or the null hypothesis is not rejected for the primary endpoint of PFS);
- c) the participant can obtain medication from a government-sponsored or private health program.

In all cases Exelixis will follow local regulations. Exelixis will work with study investigators to act in the best interest of subjects.

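### Protocol 3.6.1 makes placebo assignment at study-wide unblinding a reason to stop all study treatment, without limiting it to the oral component, so active nivolumab could end in control subjects who still benefit

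*Protocol*

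**What the plan says.** Protocol 3.6.1 opens with a general rule: "Subjects will receive study treatment until treatment discontinuation for any of the reasons listed below". The list is introduced with "The following are possible reasons for discontinuation of all study treatment", and its last bullet reads "Subject is determined to have been randomized to receive placebo following study-wide unblinding".

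Control treatment is more than placebo. Under 3.4 both arms receive four doses of nivolumab plus ipilimumab and then flat-dose nivolumab: "Nivolumab will be administered for a maximum of 2 years".

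Four other places bear on what happens after unblinding:

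- **5.3** tells investigators and subjects the assignment so that treatment can be decided, and adds: "Protocol procedures and assessments will continue without change".
- **5.5** says: "In the Maintenance Phase, subjects on active study treatment will continue to receive study treatment until a criterion for protocol-defined discontinuation has been met", citing 3.6.1. Appendix B says much the same.
- **6.3** says that after study completion, subjects who still benefit "may be eligible to receive Exelixis-supplied study treatment for the maximum treatment duration specified in" Section 6.2. Under 6.2, nivolumab runs for up to 2 years while the subject benefits.
- **The Maintenance Phase schedule in Appendix B** lists nivolumab with a 2-year cap and does not split it by arm. Its stopping rule is again a criterion in 3.6.1.

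**The concern.** Once the study is unblinded, a control subject has no reason to keep taking placebo tablets. Stopping those is sensible. The bullet, however, stands in a list about all study treatment and does not say that only the tablets stop. A site that applies it as written would also stop nivolumab in a control subject who is still benefiting and still inside the 2-year limit. An experimental-arm subject in the same position would continue.

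This concerns patient care and internal consistency. A negative PFS result is itself Study Completion under 3.6.3. In that case 6.3 opens the door to continued treatment, while the 3.6.1 bullet can be read as closing it for one arm only.

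**Working it through.** **Step 1: is the bullet operative?** The lead-in calls the reasons possible ones, but that does not make each of them optional. Two other bullets in the same list are mandatory stops elsewhere in the protocol: pregnancy (8.5.1) and unblinding of an individual subject (3.5.2). The opening sentence of 3.6.1 and the cross-references from 5.5, Appendix B and the Maintenance schedule also treat the list as the stopping rule.

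**Step 2: what does the literal reading do?** The Maintenance Phase can begin only after unblinding (5.5). Read literally, every control subject already meets a 3.6.1 criterion on that day. The nivolumab line in the schedule would then apply to the experimental arm only, and no section says that this is intended.

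**Step 3: where is the tension?**

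| Place | Bearing on control-arm nivolumab after unblinding |
|---|---|
| 3.6.1 bullet | Stops all study treatment if read literally |
| 5.3 | Continues procedures and assessments; does not promise drug |
| 6.2 | Nivolumab up to 2 years while benefiting, either arm |
| 6.3 | Benefiting subjects of either arm may be eligible |
| Maintenance schedule | Lists nivolumab without splitting by arm, but defers to 3.6.1 |

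**Step 4: when could it matter?** The inputs are from Protocol 9.5: 40 subjects per month for 21 months, 840 subjects randomized 1:1, exponential OS with medians of 48 and 65.8 months. Dropout is ignored. With λ = ln 2 / median, expected deaths in one arm at month t ≥ 21 are 20 × [21 − (exp(−λ(t−21)) − exp(−λt))/λ].

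- Check against the plan: at t = 69.3 this gives about 239.6 control and 193.4 experimental deaths, total 433. The protocol states 69 months.
- Solving for the other looks: 117 deaths (27%) at month 22.8; 217 (50%) at 34.8; 281 (65%) at 43.6; 325 (75%) at 50.1; 346 (80%) at 53.6.
- The last subject enters at 840/40 = month 21 and leaves the nivolumab window at about 21 + 24 = month 45.

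Control subjects enter at 20 per month. The number inside the window is an upper bound on those still receiving nivolumab, because it ignores everyone who stopped earlier:

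- Month 23 (planned primary PFS analysis and first OS interim): all 420, since even the first subject is only 23 months in.
- Month 34.8: (45 − 34.8) × 20 ≈ 205.
- Month 43.6: (45 − 43.6) × 20 = 28.
- Month 45 and later: none. The 75% look, the 80% look and final OS all fall outside.

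**Step 5: which unblinding routes remain?** After a positive PFS result, 5.3 delays unblinding until OS is rejected or the final OS analysis is done. Protocol 9.6 does not expect rejection at the first OS interim. SAP Table 14 keeps the second interim at 50% if the first falls below 30% information. It moves the second to 65% if the first is at 30 to <40%, to 75% at 40 to <50%, and to 80% at 50 to 65%. On the design calendar, the second interim is therefore inside the window only if the first is below 40% information. The futility look was planned at about 100 PFS events. SAP 4.8.1 reports about 209 events with the study still blinded, so that route appears to have passed.

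**Step 6: is the negative-PFS route real?** SAP 4.8.1 gives a minimum follow-up of 15.6 months in the first 550 subjects. Anyone randomized later had no more than that, so was at least 24 − 15.6 = 8.4 months short of the 2-year limit. If all 840 were enrolled, that is (840 − 550)/2 = 145 control subjects under 1:1 allocation. This shows who was inside the window, not who was still on nivolumab.

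**The case against.** The best case for leaving the text alone has three parts.

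First, nothing is flatly contradicted. Section 5.3 continues procedures and assessments and leaves treatment to be decided once assignments are known. Section 6.3 only says subjects may be eligible. The Maintenance schedule names 3.6.1 as its own stopping rule. All of this stands, and it rules out calling the bullet a contradiction of those sections.

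Second, component-level thinking is present nearby. The side-effects bullet allows one component to continue while another stops. The paragraph after the list sends cabozantinib and nivolumab/ipilimumab to separate discontinuation criteria. Section 5.5 speaks of active treatment. A sensible site might well stop only the tablets. But the permission to continue one component is written into the side-effects bullet alone, and a careful reader could take its absence from the placebo bullet as deliberate.

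Third, the harm is bounded. The sponsor can issue instructions at unblinding. Section 6.3 commits it to work with investigators in subjects' best interest and allows a rollover study or another mechanism. The same section lets the sponsor end supply if the "study is declared futile or the null hypothesis is not rejected for the primary endpoint of PFS". Nivolumab plus ipilimumab is approved in the US and EU for this population (1.7.1), so a stop there would end study supply and not necessarily therapy. This stands and keeps the severity low. The trial also enrols in Latin America and Asia, where the documents do not give approval status by country, so study supply may matter more there.

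**Conclusion.** The point holds as a minor wording fault in an operative rule. As written, 3.6.1 can end active nivolumab for every control subject at unblinding. That pulls against 6.2 and 6.3.

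It has practical effect only if unblinding comes while control subjects are within 2 years of starting treatment: after a negative PFS result, or after OS rejection at an early interim. Under the design assumptions that means before about month 45. The calendar is indicative only. SAP 4.8.1 shows PFS events arriving more slowly than planned, and faster deaths would bring the OS looks forward.

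A reader might infer more than the documents support:

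- **That the protocol contradicts itself.** It does not, for the reasons given on 5.3, 6.3 and the schedule.
- **That withdrawing nivolumab from controls is the intended policy, or that the bullet is plainly a slip.** Neither can be shown. Section 3.5.2 deliberately stops all treatment after individual unblinding, so an all-stop intent cannot be excluded, but no section states one for study-wide unblinding.
- **That a known number of subjects would lose treatment.** The figures above bound who is inside the window. Time on nivolumab is not given, so no count of affected subjects follows.
- **That the trial's inference is at risk.** It is not. Unblinding after negative PFS, OS rejection or final OS comes once formal testing has ended, so alpha, power and estimands are unaffected.

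**What to change.** Move the bullet out of the all-treatment list and replace it with:

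*Following study-wide unblinding, subjects found to have been randomized to placebo discontinue the oral component only; nivolumab may continue to the 2-year maximum per Section 6.2 while the subject benefits, subject to Section 6.3.*

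Add a matching sentence in 5.5 and Appendix B. It should mention nivolumab only: the Maintenance schedule has no ipilimumab line, and scheduled ipilimumab ends at W10D1, so adding ipilimumab text there would create a new mismatch.

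If the sponsor does intend a full stop for control subjects, the protocol should say so and align 6.3 and the Maintenance schedule.

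The cost is a wording change in the next amendment, with IRB/EC submission as required under Section 14 across about 180 sites. No visits, data or analyses are added. If unblinding comes before an amendment, a sponsor instruction to sites could carry the same sentence in the meantime.
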